7. ADVERSE EVENTS AND REPORTING PROCEDURES

7.1. Potential Adverse Events

The patients will be injected with ¹⁸F-FTC-146, which is an investigational drug. An IND application has previously been filed with FDA (IND ████████ IND-holder [name]). Toxicity studies performed by unbiased party have shown no treatment related toxicity at 3 and 15 days after treatment with a single dose (250-fold the expected clinical dose) in a single rodent species. There are no known pharmacological risks of the drug. However, there is risk of radiation dose as described below.

This research study involves exposure to radiation from two 10 mCi +/- 20% doses of ¹⁸F-FTC-146. The radiation exposure from two 10 mCi +/- 20% doses of ¹⁸F-FTC-146 is

maximally 19.2 mSv, which is approximately equal to 38% of the limit that radiation workers (for example, a hospital X-ray technician) are allowed to receive in 1 year. This amount of radiation involves minimal risk and is necessary to obtain the research information desired.

7.2. Adverse Event Reporting

Adverse events will be graded according to CTCAE v5.0. Both Serious and Non-Serious Adverse Events will be clearly noted in source documentation and listed on study-specific Case Report Forms (CRFs). The Protocol Director (PD) or designee will assess each Adverse Event (AE) to determine whether it is unexpected according to the Informed Consent, Protocol Document, or Investigator's Brochures, and related to the investigation. **Only adverse events related to PET/CT procedure will be captured.** All Serious Adverse Events (SAEs) will be tracked until resolution and 30 days after the last investigational scan.

8. REGULATORY CONSIDERATIONS

8.1. Institutional Review of Protocol

The protocol, the proposed informed consent and all forms of participant information related to the study (eg, advertisements used to recruit participants, questionnaires) will be reviewed and approved by the Stanford IRB and Scientific Review Committee (SRC). Any changes made to the protocol will be submitted as a modification and will be approved by the IRB and SRC prior to implementation. The Protocol Director will disseminate the protocol amendment information to all participating investigators.

8.2. Data Management Plan

The research coordinator will be responsible for database records of subject data. The data will be kept in an OnCore online database, under password protection with access limited to specific areas of the database. A chart with all of the relevant research subject information will be maintained for each subject by the research coordinator. Subject charts will be reviewed by Stanford PI and Study Coordinator for yearly audits.

8.3. Data and Safety Monitoring Plan

The Protocol Director will oversee the conduct of the trial.

The Stanford Cancer Institute Data and Safety Monitoring Committee (DSMC) will audit study related activities at least annually in accordance with the DSMC SOP to determine whether the study has been conducted in accordance with the protocol, local standard operating procedures, FDA regulations, and Good Clinical Practice (GCP). This may include review of regulatory binders, case report forms, medical notes, eligibility checklists, and source documents. In addition, the DSMC will regularly review serious adverse events and protocol deviations associated with the research to ensure the protection of human subjects. Results of DSMC audits will be communicated to the IRB and the appropriate regulatory authorities at the time of continuing review, or in an expedited fashion, as needed.

9. MEASUREMENTS

9.1. Primary and Secondary Endpoints

1. Histologically-determined percentage of necrosis in post-chemotherapy resected tumor.
2. Pre- and post-treatment SUVmax in tumor ROI, and the pre-post percent change.
3. Pre- and post-treatment pain score, and the pre-post difference.

9.2. Measurement Methods

1. Assessment of necrosis in osteosarcoma specimens is performed by subspecialized bone-soft tissue pathologists and pediatric pathologists. The resection specimen is sequentially sliced at 0.5 cm intervals to yield a series of macrosections. A full single macrosection, including tumor, is entirely submitted for microscopic evaluation with the coordinates of histologic sections mapped to a photograph of the macrosection. Histologic assessment of the proportion of viable tumor is performed on H&E-stained sections.
2. PET SUVmax will be measured in an ROI drawn over the lesion (based on CT).
3. Patients will rate pain level using PROMIS (Patient-Reported Outcome Measurement Information System) Questionnaires.

9.3. Measurement Time Points

1. Imaging and pain measurements will be made just before and after treatment (3 cycles of chemotherapy).
2. Tumor histology will be measured on the post-chemotherapy resected tumor, after the second PET/CT scan.

10. STATISTICAL CONSIDERATIONS

10.1. Statistical Design

This is an one-arm, non-randomized prospective cohort study.

10.2. Descriptive Statistics and Exploratory Data Analysis

Descriptive statistics and correlations will be calculated consisting of the means, medians, and standard deviations of:

1. Histologically determined percentage of necrosis in post-chemotherapy resected tumor.
2. Pre- and post-treatment SUVmax in tumor region of interest (ROI), and the pre-post percent change.
3. Pre- and post-treatment pain score, and the pre-post difference.

10.3. Primary Analysis

10.3.1. Analysis Population

All enrolled subjects.

10.3.2. Analysis Plan

1. The following will be recorded for each patient
 - (a) the histological percentage of necrosis and
 - (b) the percent reduction in SUVmax.
2. The histological percent necrosis will be plotted against SUVmax percent reduction to calculate rank correlation.

10.4. Secondary Analysis

10.4.1. Analysis Population

All enrolled subjects.

10.4.2. Analysis Plan

1. The following will be recorded for each patient
 - (a) the post-treatment reduction in pain score.
 - (b) the percent reduction in SUVmax.
2. The reduction in pain score will be plotted against SUVmax reduction to calculate rank correlation.

10.5. Sample Size

Preliminary approval for this study is for 5 subjects only. An eventual sample size of 20 will provide 90% power at one-sided 5% error to detect a correlation as low as 0.60.

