10.7. Criteria for future studies

This study will be judged to be successful if both:

- (a) the correlation between necrosis and PET signal reduction is ≥ 0.60 .
- (b) the correlation between pain reduction and PET signal reduction is ≥ 0.60 .

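### The 90% power stated for an eventual 20 subjects fits a Pearson test; a Spearman test has about 88% or 86%, depending on the scale of the 0.60

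*Combined protocol and SAP*

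**What the plan says.** Section 10.5 gives the power statement, and the Sample Size entry of the synopsis repeats it: "An eventual sample size of 20 will provide 90% power at one-sided 5% error to detect a correlation as low as 0.60". Neither place names the coefficient, the test or the null value. Section 10.5 also says: "Preliminary approval for this study is for 5 subjects only".

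The analysis sections plan rank correlations only. For the primary analysis, 10.3.2 says: "The histological percent necrosis will be plotted against SUVmax percent reduction to calculate rank correlation". For the secondary analysis, 10.4.2 says: "The reduction in pain score will be plotted against SUVmax reduction to calculate rank correlation". The synopsis plans the same. None of these places says whether Spearman or Kendall is meant, and none describes a hypothesis test.

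Section 10.7 uses the value 0.60 again. Both observed correlations (necrosis with signal reduction, and pain reduction with signal reduction) must reach it for the study to count as successful. The coefficient is not named there either.

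**The concern.** A reader of 10.5 will take the 90% as the power of the analysis in 10.3.2 and 10.4.2, because no other correlation analysis is planned. The usual calculation for a correlation is for Pearson's coefficient, and a rank test has somewhat less power when the data are bivariate normal. If the 90% comes from a Pearson calculation, the planning figure and the planned statistic do not match.

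What is at stake is modest. The sentence is the documents' only quantitative justification for a sample size, and it would be carried forward if the study were extended to 20. The same 0.60 is the threshold in 10.7, and its meaning depends on the coefficient.

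**Working it through.** **Inputs.** From 10.5: n = 20, one-sided alpha 0.05, correlation 0.60, stated power 0.90. From 10.3.2 and 10.4.2: a rank correlation.

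**Assumptions, not stated in the documents.** The null correlation is zero, the data are bivariate normal, there are no ties, and all 20 pairs are complete.

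**Step 1: reproduce the stated figure with a Pearson test.**

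- Fisher z: Φ(atanh(0.60) × √(20 − 3) − 1.645) = Φ(0.6931 × 4.123 − 1.645) = Φ(1.213) = 0.887.
- Fisher z with the bias term ρ/(2(n − 1)) = 0.60/38 = 0.0158 added to 0.6931: 0.899.
- Simulated t test (critical r = 0.378): 0.903 to 0.904.
- Two-sided 5% by Fisher z: 0.815, so the one-sided test is the variant that matches.

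The 90% therefore reproduces for a Pearson test. That it was calculated this way is an inference, since the documents name no method.

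**Step 2: put 0.60 on each scale.** Under bivariate normality:

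- Pearson 0.60 corresponds to Spearman (6/π) × arcsin(0.60/2) = 0.582.
- Spearman 0.60 corresponds to Pearson 2 × sin(π × 0.60/6) = 0.618.

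**Step 3: power of the one-sided 5% Spearman test at n = 20, by simulation.** The ranges cover separate runs and two cut-offs: the t-based cut-off (0.378, simulated size 0.050) and a slightly stricter one from the simulated null distribution (0.3805, size 0.049).

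| Meaning of 0.60 | Simulated power | Fisher z, variance 1.06/(n − 3) |
|---|---|---|
| Population Spearman | 0.878 to 0.880 | 0.871 |
| Underlying Pearson | 0.854 to 0.857 | 0.846 |

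The approximation in the first row is Φ(0.6931 × √(17/1.06) − 1.645) = Φ(1.131) = 0.871.

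The shortfall against 0.90 is about 0.90 − 0.88 = 0.02 on the Spearman scale and 0.90 − 0.856 = 0.044 on the Pearson scale.

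**Step 4: what would give 90%.**

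- With 20 pairs, the population Spearman correlation would have to be about 0.62 (power 0.890 at 0.61 and 0.902 to 0.903 at 0.62).
- With 0.60 as a Spearman correlation: about 0.895 at n = 21 and 0.908 at n = 22, so 22 pairs.
- With 0.60 as a Pearson correlation: 0.888 at n = 22 and 0.902 at n = 23, so 23 pairs.

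**Step 5: Kendall as the alternative rank test, n = 20.** Power is about 0.875 at a population Spearman correlation of 0.60 and 0.851 to 0.853 at Pearson 0.60, so the shortfall does not depend on choosing Spearman as the test. If 0.60 is itself a tau, it corresponds to Pearson sin(π × 0.60/2) = 0.809, a much stronger association, and power is 0.996.

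**The case against.** The strongest reply is that nothing was miscalculated. The 90% is correct for a Pearson test, and on the more natural reading, with 0.60 as a Spearman correlation, the gap is 2 points. Plain Fisher z and simulation already differ by 1.6 to 1.7 points for the same Pearson test (0.887 against 0.903 to 0.904). Section 2.4 describes a feasibility study, and a one-sentence planning figure there is seldom held to tighter precision. The direction also depends on a choice the documents do not make: with 0.60 as a tau, the statement is conservative. Finally, no decision turns on the figure. Only 5 subjects are approved, and the rule in 10.7 is a threshold on the observed correlations, not a significance test.

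Most of this stands, and it is why the point is minor. It does not rescue the figure. None of the rank readings examined gives 90%: the results are about 86%, about 88% or above 99%. On the scale where the 90% reproduces, the gap is more than 4 points and 3 pairs.

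The no-ties assumption also deserves caution. Pain is scored from items with five response levels (Appendix B), so ties are likely in the secondary analysis, and the documents give no data to quantify their effect. Normality matters less: other forms of dependence (Frank, Clayton, t with 4 degrees of freedom) at a population Spearman correlation of 0.60 gave about 0.86 to 0.88.

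**Conclusion.** The concern holds, as a minor one. The power stated in 10.5 and the synopsis is not the power of a Spearman test with 20 pairs. That is about 88% at a population Spearman correlation of 0.60 and about 86% at an underlying Pearson correlation of 0.60, so the statement is about 2 to 4 points too high.

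Confidence in the arithmetic is high. The conclusion rests on reading the one-sided 5% error as a test of zero correlation and on the assumptions listed in the working. It would reverse only if 0.60 were meant as a Kendall tau. It concerns a possible extension to 20 and has no bearing on the analysis of the 5 approved subjects.

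**What to change.** Name the rank coefficient in 10.3.2 and 10.4.2, and use the same one for the power statement in 10.5 and the synopsis and for the 0.60 threshold in 10.7. Restate the power for that coefficient, with its assumptions, and limit it to the possible extension. If Spearman is meant, wording such as this would do:

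> If enrolment is later extended to 20 subjects, all with complete pairs, a one-sided 5% test of zero Spearman correlation has about 88% power at a population Spearman correlation of 0.60 (about 86% at an underlying Pearson correlation of 0.60), assuming bivariate normal data without ties. Power reaches 90% at a Spearman correlation of about 0.62. These figures do not apply to the 5 subjects currently approved.

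If Kendall's tau is meant, give the power for tau and say whether 0.60 is on the tau scale.

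The cost is wording in the synopsis, 10.3.2, 10.4.2, 10.5 and 10.7. The only drawback is that the stated power is 2 to 4 points less favourable. No increase in sample size is requested.

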10.6. Accrual estimates

Stanford treats roughly 8 to 10 adult osteosarcoma patients per year. We expect to be able to recruit at least half of them.

10.7. Criteria for future studies

This study will be judged to be successful if both:

- (a) the correlation between necrosis and PET signal reduction is ≥ 0.60 .
- (b) the correlation between pain reduction and PET signal reduction is ≥ 0.60 .

Appendix A: Inclusion/Exclusion Criteria Checklist

*All subject files must include supporting documentation to confirm subject eligibility. The method of confirmation can include, but is not limited to, laboratory test results, radiology test results, subject self-report, and medical record review.

Protocol Information

Protocol Title:	A Phase 2 Study of ¹⁸ F-FTC-146 PET/CT in Patients with Newly-Diagnosed Osteosarcoma
eProtocol number: OnCore number:	IRB-52746 SARCOMA0041
Principal Investigator:	[name]

Subject Unique ID: SAR41- ____ ____			
Inclusion Criteria (From IRB-approved protocol)	Yes	No	Supporting Documentation*
1. Patients with biopsy-proven osteosarcoma requiring local surgical intervention.			
2. Age ≥ 18 years			
3. ECOG ≤ 2			
4. Ability to understand and the willingness to sign a written informed consent document.			
Exclusion Criteria (From IRB-approved protocol)			
1. Chemotherapy in the past 2 months.			
2. Prior history of reaction to ¹⁸ F-FTC-146.			
3. Pregnancy or nursing patients			

IV. Statement of Eligibility

This subject is [**eligible** / **ineligible**] for participation in the study.

Study Coordinator printed name:	Date:
Signature:	

Investigator printed name:	Date:
Signature:	

Triple-check reviewer printed name:	Date:
Signature:	

**Appendix B: PROMIS (Patient-Reported Outcomes Measurement Information System)
Questionnaires**

Pain Intensity – Scale

Please respond to each item by marking one box per row.

In the past 7 days...		Had no pain	Mild	Moderate	Severe	Very severe
PAINQU6	How intense was your pain at its worst?....	 1	 2	 3	 4	 5
PAINQU8	How intense was your average pain?.....	 1	 2	 3	 4	 5
		No pain	Mild	Moderate	Severe	Very severe
PAINQU21	What is your level of pain right now?.....	 1	 2	 3	 4	 5

Intensidad del dolor – Cuestionario abreviado 3a

Responda a cada pregunta marcando una casilla por línea.

En los últimos 7 días ...		No tuve dolor	Muy poco	Moderado	Intenso	Muy intenso
						
PAINQU6	¿Qué intensidad tuvo el dolor en su peor momento?.....	 1	 2	 3	 4	 5
PAINQU8	¿Qué intensidad tuvo el dolor que sintió en su punto medio?	 1	 2	 3	 4	 5
		Ningún dolor	Muy poco	Moderado	Intenso	Muy intenso
						
PAINQU21	¿Cuál es su nivel de dolor en este momento?.....	 1	 2	 3	 4	 5

Pain Interference – Short Form 4a

Please respond to each question or statement by marking one box per row.

In the past 7 days...		Not at all	A little bit	Somewhat	Quite a bit	Very much
PAININ9	How much did pain interfere with your day to day activities?.....	 1	 2	 3	 4	 5
PAININ22	How much did pain interfere with work around the home?.....	 1	 2	 3	 4	 5
PAININ31	How much did pain interfere with your ability to participate in social activities?	 1	 2	 3	 4	 5
PAININ34	How much did pain interfere with your household chores?	 1	 2	 3	 4	 5

Efectos del dolor – Cuestionario abreviado 4a

Responda a cada pregunta o enunciado marcando una casilla por línea.

En los últimos 7 días ...		Nada	Un poco	Algo	Mucho	Muchísimo
PAININ9 1	¿En qué medida el dolor interfirió en sus actividades diarias?	 1	 2	 3	 4	 5
PAININ22 2	¿En qué medida el dolor interfirió en el trabajo en el hogar?	 1	 2	 3	 4	 5
PAININ31 3	¿En qué medida el dolor interfirió en su capacidad para participar en actividades sociales?.....	 1	 2	 3	 4	 5
PAININ34 4	¿En qué medida el dolor interfirió en sus tareas domésticas?	 1	 2	 3	 4	 5
